6.2.5 Expedited Reporting Requirements for Serious Adverse Events

All SAEs must be reported within 24 hours of discovery. All initial SAE/AES/ reports and follow-up information will be reported using the protocol-specific electronic data capture system. If electronic SAE/AES/ reporting is not available, paper SAE/Product Complaint forms must be emailed or faxed to Acerta Pharma Drug Safety, or designee. Acerta

Pharma may request follow-up and other additional information from the investigator (eg, hospital admission/discharge notes and laboratory results).

All deaths should be reported with the primary cause of death as the AE term, as death is typically the outcome of the event, not the event itself. The primary cause of death on the autopsy report should be the term reported. Autopsy and postmortem reports must be forwarded to Acerta Pharma Drug Safety, or designee, as outlined above.

If study drug is discontinued because of an SAE/AES/, this information must be included in the SAE/AES/ report.

An SAE/AES/ may qualify for mandatory expedited reporting to regulatory authorities if the SAE/AES/ is attributable to the investigational product and is not listed in the current Investigator Brochure (ie, an unexpected event). In this case, Acerta Pharma Drug Safety/Designee will forward a formal notification describing the SAE/AES/ to all investigators. Each investigator must then notify his or her IRB/IEC of the SAE/AES/.

| Drug Safety Contact Information | |
|---------------------------------|-----|
| Fax: | PPD |
| Email: | |

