2.0 STUDY OBJECTIVES

2.1 PRIMARY OBJECTIVE

To characterize the safety profile of *acalabrutinib* in subjects with relapsed or refractory ABC DLBCL

2.2 SECONDARY OBJECTIVES:

- To characterize the PK of *acalabrutinib*
- To evaluate the PD effects of *acalabrutinib*
- To evaluate the activity of *acalabrutinib* as measured by response rate, duration of response, time-to-next treatment, and progression-free survival

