3.2.2 Safety Parameters

The safety of *acalabrutinib* will be characterized by the type, frequency, severity, timing of onset, duration, and relationship to study drug of any treatment-emergent AEs or abnormalities of laboratory tests; SAEs; or AEs leading to discontinuation or dose reduction of study treatment.

For consistency of interpretation, AEs will be coded using the Medical Dictionary for Regulatory Activities (MedDRA), and the severity of AEs and laboratory abnormalities will be graded using the Common Terminology Criteria for Adverse Events (CTCAE), Version 4.03. Standard definitions for seriousness will be applied (see [Section 6.1](#)).

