6.1 DEFINITIONS

6.1.1 Adverse Events

An AE is any unfavorable and unintended sign, symptom, or disease temporally associated with the use of an investigational (medicinal) product or other protocol-imposed intervention, regardless of attribution.

This includes the following:

- AEs not previously observed in the subject that emerge during the protocol-specified AE reporting period, including signs or symptoms associated with DLBCL that were not present before the AE reporting period (see [Section 6.2.1](#))

- Complications that occur as a result of protocol-mandated interventions (eg, invasive procedures such as biopsies)
- Preexisting medical conditions (other than the condition being studied) judged by the investigator to have worsened in severity or frequency or changed in character during the protocol-specified AE reporting period.

Abnormal laboratory values should not be reported as AEs; however, any clinically significant laboratory values (defined as requiring treatment, discontinuation from the study, or dose modification) should be reported as AEs.

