6.1.2 Serious Adverse Event

The terms “severe” and “serious” are not synonymous. Severity (or intensity) refers to the grade of an AE (see below). “Serious” is a regulatory definition and is based on subject or event outcome or action criteria usually associated with events that pose a threat to a subject’s life or functioning. Seriousness (not severity) serves as the guide for defining regulatory reporting obligations from the sponsor to applicable regulatory authorities.

An AE should be classified as an SAE if it meets any 1 of the following criteria:

- It results in death (ie, the AE actually causes or leads to death).
- It is life-threatening (ie, the AE, in the view of the investigator, places the subject at immediate risk of death. It does not include an AE that, had it occurred in a more severe form, might have caused death).
- It requires or prolongs in-patient hospitalization.
- It results in persistent or significant disability/incapacity (ie, the AE results in substantial disruption of the subject’s ability to conduct normal life functions).
- It results in a congenital anomaly/birth defect in a neonate/infant born to a mother exposed to the investigational product.
- It is considered a significant medical event by the investigator based on medical judgment (eg, may jeopardize the subject or may require medical/surgical intervention to prevent 1 of the outcomes listed above).

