6.1.3 Severity

Definitions found in the CTCAE version 4.03 or higher will be used for grading the severity (intensity) of AEs. The CTCAE displays Grades 1 through 5 with unique clinical descriptions of severity for each referenced AE. Should a subject experience any AE not listed in the CTCAE, the following grading system should be used to assess severity:

- Grade 1 (Mild AE) – experiences which are usually transient, requiring no special treatment, and not interfering with the subject’s daily activities

- Grade 2 (Moderate AE) – experiences which introduce some level of inconvenience or concern to the subject, and which may interfere with daily activities, but are usually ameliorated by simple therapeutic measures
- Grade 3 (Severe AE) – experiences which are unacceptable or intolerable, significantly interrupt the subject's usual daily activity, and require systemic drug therapy or other treatment
- Grade 4 (Life-threatening or disabling AE) – experiences which cause the subject to be in imminent danger of death
- Grade 5 (Death related to AE) – experiences which result in subject death

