6.2.2 Assessment of Adverse Events

Investigators will assess the occurrence of AEs and SAEs at all subject evaluation timepoints during the study. All AEs and SAEs whether volunteered by the subject, discovered by study personnel during questioning, or detected through physical examination, or other means will be recorded in the subject's medical record and on the AE eCRF and, when applicable, on an SAE/Product Compliant form.

Disease progression itself is not considered an AE; however, signs and symptoms of disease progression may be recorded as AEs or SAEs.

Symptomatic deterioration may occur in some subjects. Symptomatic deterioration is when progression is evident in the subject's clinical symptoms and the investigator may elect not to perform further disease assessments.

Each recorded AE or SAE will be described by its duration (ie, start and end dates), severity, regulatory seriousness criteria, if applicable, suspected relationship to the study drug (see following guidance), and any actions taken. The relationship of AEs to the study drug will be assessed by means of the question: 'Is there a reasonable possibility that the event may have been caused by the study drug?' Answer Yes or No.

See [Appendix 3](#) for more detail on assessing relationship.

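### Protocol Sections 6.2.5 and 6.2.2 give conflicting rules for recording a death from DLBCL progression, so the Grade 5 AE and SAE counts depend on which section a site follows

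*Protocol*

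**What the plan says.** Section 6.2.5, on expedited reporting, states: "All deaths should be reported with the primary cause of death as the AE term". It adds, for cases with an autopsy: "The primary cause of death on the autopsy report should be the term reported". Neither sentence exempts death from the lymphoma being treated.

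Section 6.2.2, on assessing AEs, states: "Disease progression itself is not considered an AE; however, signs and symptoms of disease progression may be recorded as AEs or SAEs".

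Three further definitions bear on the result:

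- Section 6.1.2 gives the fatal criterion for an SAE: "It results in death (ie, the AE actually causes or leads to death".
- Section 6.1.3 gives the fatal grade: "Grade 5 (Death related to AE) – experiences which result in subject death".
- Section 6.1.1 defines AEs as "including signs or symptoms associated with DLBCL that were not present before the AE reporting period", among other things.

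The sole primary objective (Section 2.1) is "To characterize the safety profile of *acalabrutinib* in subjects with relapsed or refractory ABC DLBCL". Section 3.2.2 describes that profile through the type, frequency and severity of treatment-emergent AEs, among other attributes, and through "abnormalities of laboratory tests; SAEs; or AEs leading to discontinuation or dose reduction of study treatment". Section 5.5.1 tabulates AEs by MedDRA term, by CTCAE severity and by relationship to study drug.

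**The concern.** A death from progression falls under both rules, and they give different answers. If a site enters DLBCL as the AE term because it was the cause of death, it has recorded progression as an AE, which Section 6.2.2 rules out. If it enters no AE because progression is not one, it has not done what Section 6.2.5 asks for every death. If it enters a fatal symptom, it has used the option in Section 6.2.2, but the term need not be the primary cause of death.

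These are collection rules applied by investigators at about 9 sites in up to 4 countries (Section 3.1). If practice differs, disease outcome enters the AE and SAE tables for some subjects and not for others. An analysis plan can only work around records already made inconsistently. In a single-arm safety study of about 20 subjects, a few such records would visibly change the fatal-AE and SAE counts.

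Deaths of this kind are foreseeable from the protocol. Section 1.1 calls the prognosis poor when initial therapy fails, and half of the planned subjects are refractory (Section 3.1). Subjects with definitive progression leave treatment (Section 3.8). AE reporting then continues until 30 days after the last dose or the start of new anticancer therapy, whichever comes first (Section 6.2.1).

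**Working it through.** **Step 1. Apply each rule to one case:** a treated subject whose primary cause of death, inside the AE reporting period, is DLBCL progression.

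| Rule followed | AE term | Grade | SAE | Counted as fatal AE |
|---|---|---|---|---|
| Section 6.2.5 | DLBCL or progression | 5 (Section 6.1.3) | Yes (Section 6.1.2) | Yes |
| Section 6.2.2, option to record a symptom used | A sign or symptom | 5 | Yes | Yes, under another term |
| Section 6.2.2, option not used | None | None | No | No |

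**Step 2. Look for a rule of precedence.** There is none. Section 6.2.3 deals with malignant tumors as AEs but is limited to new malignancies and excludes the tumor under study. The conflict is therefore left open.

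**Step 3. Size per death.** The protocol states no figure that depends on this point. Its sample size is explicitly not based on power (Section 5.4), so there is nothing to reproduce. Inputs: n = 20 planned subjects (Section 5.4) and a safety set of all enrolled subjects with at least one dose (Section 5.2). The change in the fatal-AE rate per reclassified death is 1/n = 1/20 = 5 percentage points. The subject-level SAE rate changes by up to 5 points, or by 0 if that subject already has another SAE.

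**Step 4. Illustration over an assumed number of deaths.** The documents give no count of DLBCL deaths in the reporting period, so k is an assumption. Suppose there are no other fatal AEs. Then 6.2.2 without a recorded symptom gives 0/20 = 0% (exact 95% interval 0 to 16.8%), and 6.2.5 gives k/20:

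| k (assumed) | k/20 | Exact 95% interval |
|---|---|---|
| 1 | 5% | 0.1 to 24.9% |
| 2 | 10% | 1.2 to 31.7% |
| 4 | 20% | 5.7 to 43.7% |
| 6 | 30% | 11.9 to 54.3% |

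**Step 5. Chance that the conflict arises at all.** With an assumed probability p per subject of such a death, P(at least one) = 1 − (1 − p)^20.

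- p = 10%: 1 − 0.9^20 = 87.8%, expected number 20 × 0.1 = 2
- p = 20%: 1 − 0.8^20 = 98.8%, expected number 4
- p = 30%: 1 − 0.7^20 = 99.9%, expected number 6

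Across this assumed range, at least one affected death is likely.

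**The case against.** The best defence is that the sentence in Section 6.2.5 is mainly about choosing a term. It explains that death is usually an outcome and not an event, so sites should not enter death itself. Section 6.1.2 likewise speaks of an AE that leads to death, which presupposes an AE. On that narrower reading, 6.2.5 would not turn progression into an AE. The reading is available, but the sentence covers all deaths and carries no exception, so a site following the text has no reason to adopt it.

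Second, a lymphoma death entered under 6.2.5 would normally carry a disease term and could be judged unrelated under Appendix 3. Because Section 5.5.1 tabulates by term and by relationship, a reader could then pick it out. That helps where the death was entered, but not where a site entered no AE. The eCRF completion guidelines mentioned in Section 7.5 may also address the matter. They are not at hand, and they would not remove the contradiction from the protocol.

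Third, a reader might infer more than the text supports:

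- *That Section 6.1.1 also contradicts Section 6.2.2.* It does not. Section 6.1.1 counts DLBCL signs and symptoms that are new in the reporting period and leaves worsening of the studied condition out of its item on preexisting conditions. The permissive wording in 6.2.2 covers signs and symptoms of progression generally. A site that records the new ones satisfies both sections. The wording is loose, not contradictory.
- *That a fatal-AE rate is the primary safety result.* The protocol names no such endpoint. The profile is descriptive, with no comparator and no hypothesis test, so no decision rule rests on this rate.
- *That the rate will shift by 10 to 30 points.* This requires 2 to 6 affected deaths, which is assumed. It also requires every site on one reading compared with every site on the other, and no fatal symptom recorded in place of progression.

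**Conclusion.** The contradiction between Sections 6.2.5 and 6.2.2 stands for deaths due to DLBCL progression and should be removed. The two collection rules give different records for the same event, and those records feed the Grade 5 AE and SAE counts that contribute to the primary safety objective.

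The supportable size is up to 5 percentage points in the fatal-AE rate per affected death. It is a maximum for three reasons:

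- If a fatal symptom is recorded, the count may agree and only the term differ.
- Section 3.4.3 allows replacement of subjects who do not complete Cycle 2, so the safety set may exceed 20, and 1/n is then below 5 points.
- The effect is mainly confined to the reporting period in Section 6.2.1. After that, the section asks only for SAEs or other AEs of concern thought to be related to study drug.

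The number of affected deaths is not in the documents, so the multi-death figures above are worst-case illustrations. Divergence between sites is a risk created by the text, not something the documents show to have happened.

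**What to change.** Reconcile the two sections into one recording rule for all sites. One way is to add to Section 6.2.5 that, consistent with Section 6.2.2, a death due solely to DLBCL progression is recorded on the eCRF as a death from progression and not as an AE term, and that any other cause of death is the AE term. The autopsy sentence should carry the same exception. Deaths from progression can then be counted separately from fatal AEs. How the tables are laid out can be left to the SAP.

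The cost is small: a wording change in Section 6.2.5 with a cross-reference in 6.2.2, matching eCRF guidance, and possibly recoding of a few existing records. No treatment, visit or assessment changes.

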6.2.6 Type and Duration of Follow-up of Subjects After Adverse Events

All AEs and SAEs that are encountered during the protocol-specified AE reporting period should be followed to resolution, or until the investigator assesses the event as stable, a new anticancer therapy is initiated, or the subject is lost to follow-up or withdraws consent.

6.2.7 Hy's Law

Cases where a subject shows elevations in liver biochemistry may require further evaluation, and occurrences of AST or ALT $\geq 3 \times \text{ULN}$ together with total bilirubin $\geq 2 \times \text{ULN}$ may need to be reported as SAEs. Refer to [Appendix 5](#) for further instruction on cases of increases in liver biochemistry and evaluation of Hy's law.

7.0 STUDY ADMINISTRATION AND INVESTIGATOR OBLIGATIONS

Acerta Pharma retains the right to terminate the study and remove all study materials from a study site at any time. Specific circumstances that may precipitate such termination include:

- Unsatisfactory subject enrollment with regard to quality or quantity

- Significant or numerous deviations from study protocol requirements, such as failure to perform required evaluations on subjects and maintain adequate study records
- Inaccurate, incomplete, or late data recording on a recurrent basis
- The incidence and/or severity of AEs in this or other studies indicating a potential health hazard caused by the study treatment

7.1 REGULATORY AND ETHICAL COMPLIANCE

This clinical study was designed and will be implemented in accordance with the protocol, the ICH Harmonized Tripartite Guidelines for Good Clinical Practices, applicable local regulations (including US Code of Federal Regulations Title 21 and European Directive 2001/20/EC), and the ethical principles laid down in the Declaration of Helsinki.

7.2 INSTITUTIONAL REVIEW BOARD AND INDEPENDENT ETHICS COMMITTEE

The investigator will submit this protocol, the ICF, Investigator Brochure, and any other relevant supporting information (eg, all advertising materials) to the appropriate IRB/IEC for review and approval before study initiation. A signed protocol approval page; a letter confirming IRB/IEC approval of the protocol and informed consent; and a statement that the IRB/IEC is organized and operates according to GCP and the applicable laws and regulations; **must** be forwarded to Acerta Pharma **before** screening subjects for the study. Additionally, sites must forward a signed FDA 1572 form (Statement of Investigator Form) to Acerta Pharma before screening subjects for study enrollment. Amendments to the protocol must also be approved by the IRB/IEC and local regulatory agencies, as appropriate, before the implementation of changes in this study.

7.3 INFORMED CONSENT AND PROTECTED SUBJECT HEALTH INFORMATION AUTHORIZATION

A copy of the IRB/IEC-approved ICF must be forwarded to Acerta Pharma for regulatory purposes. The investigator, or designee (designee must be listed on the Study Personnel Responsibility/Signature Log, see [Section 7.12](#)), **must** explain to each subject the purpose and nature of the study, the study procedures, the possible adverse effects, and all other elements of consent as defined in § 21CFR Part 50, and other applicable national and local regulations governing informed consent. Each subject must provide a signed and dated ICF before enrollment into this study. In the case of a subject who is incapable of providing informed consent, the investigator (or designee) must obtain a signed and dated informed consent form from the subject's legal guardian. Signed consent forms must remain in each subject's study file and be available for verification by study monitors at any time.

In accordance with individual local and national patient privacy regulations, the investigator or designee **must** explain to each subject that for the evaluation of study results, the subject's protected health information obtained during the study may be shared with Acerta Pharma and its designees, regulatory agencies, and IRBs/IECs. As the study Sponsor, Acerta Pharma will not use the subject's protected health information or disclose it to a third party without applicable subject authorization. It is the investigator's or designee's responsibility to obtain written permission to use protected health information from each subject, or if appropriate, the subject's legal guardian. If a subject or subject's legal guardian withdraws permission to use protected health information, it is the investigator's responsibility to obtain the withdrawal request in writing from the subject or subject's legal guardian **and** to ensure that no further data will be collected from the subject. Any data collected on the subject before withdrawal will be used in the analysis of study results.

7.4 SUBJECT SCREENING LOG

The investigator **must** keep a record that lists **all** subjects considered for enrollment (including those who did not undergo screening) in the study. For those subjects subsequently excluded from enrollment, record the reason(s) for exclusion.

7.5 CASE REPORT FORMS

Authorized study site personnel (see [Section 7.12](#)) will complete eCRFs designed for this study according to the completion guidelines that will be provided. The investigator will ensure that the eCRFs are accurate, complete, legible, and completed within 5 days of each subject's visit (unless required earlier for SAE reporting). The investigator will ensure that source documents that are required to verify the validity and completeness of data transcribed on the eCRFs are never obliterated or destroyed, in accordance with the record retention policies described in [Section 7.8](#).

7.6 STUDY MONITORING REQUIREMENTS

Representatives of Acerta Pharma or its designee will monitor this study until completion. Monitoring will be conducted through personal visits with the investigator and site staff as well as any appropriate communications by mail, fax, email, or telephone. The purpose of monitoring is to ensure compliance with the protocol and the quality and integrity of the data. This study is also subject to reviews or audits by the sponsor, regulatory authorities, or ethics committees.

Every effort will be made to maintain the anonymity and confidentiality of all subjects during this clinical study. However, because of the experimental nature of this treatment, the

investigator agrees to allow the IRB/IEC, representatives of Acerta Pharma, its designated agents, and authorized employees of the appropriate regulatory agencies to inspect the facilities used in this study and, for purposes of verification, allow direct access to the hospital or clinic records of all subjects enrolled into this study. This includes providing by fax, email, or regular mail de-identified copies of radiology, pathology, and/or laboratory results when requested by the sponsor. A statement to this effect will be included in the informed consent and permission form authorizing the use of protected health information.

7.7 INVESTIGATIONAL STUDY DRUG ACCOUNTABILITY

Acalabrutinib capsules must be kept in a locked limited access room. The study drug must not be used outside the context of the protocol. Under no circumstances should the investigator or other site personnel supply *acalabrutinib* capsules to other investigators, subjects, or clinics or allow supplies to be used other than as directed by this protocol without prior authorization from Acerta Pharma.

Study drug accountability records must be maintained and readily available for inspection by representatives of Acerta Pharma or regulatory authorities at any time.

Each shipment of study drug will contain a Clinical Supplies Shipping Receipt Form (CSSF) that must be appended to the site's drug accountability records. If it is used, the Drug Re-order Form (provided in the pharmacy binder) must also be included in the site's drug accountability records.

Contents of each shipment must be visually inspected to verify the quantity and document the condition of study drug capsules. Then the designated recipient completes and signs the CSSF. A copy of the signed CSSF must be faxed or emailed to Acerta Pharma at the fax number/emailing address listed on the form.

An Investigational Drug Accountability Log must be used for drug accountability. For accurate accountability, the following information must be noted when drug supplies are used during the study:

1. study identification number (ACE-LY-002)
2. subject identification number
3. lot number(s) of *acalabrutinib* dispensed for that subject
4. date and quantity of drug dispensed
5. any unused drug returned by the subject

At study initiation, the monitor will evaluate and approve the site's procedure for investigational product disposal/destruction to ensure that it complies with Acerta Pharma's

requirements. If the site cannot meet Acerta Pharma's requirements for disposal/destruction, arrangements will be made between the site and Acerta Pharma or its representative, for return of unused investigational product. Before disposal/destruction, final drug accountability and reconciliation must be performed by the monitor.

All study supplies and associated documentation will be regularly reviewed and verified by the monitor.

